9. DATA MANAGEMENT

The Clinical Epidemiology and Biostatistics Unit (CEBU) at the Royal Children's Hospital in Melbourne will be the Data Coordinating Centre for the study, and will be receiving original CRFs from central locations in the USA and the UK and entering these CRFS into a database. Boston will receive a blank duplicate of the database used in CEBU and will double enter the data using photocopied CRFs. At regular intervals the databases will be compared to identify entry errors. The following process will ensure that CEBU receives all originals and Boston receives all photocopies of CRFs.

CRFs from Australian sites will be photocopied and the originals sent to Melbourne; CRFs from European sites will be photocopied and the originals sent to Glasgow; CRFs from USA sites will photocopied and the originals sent to Boston. From Glasgow the original deidentified CRFs will be sent to Melbourne and a photocopy sent to Boston. From Boston the original deidentified CRFs will be sent to Melbourne and a copy kept in Boston. From Melbourne a deidentified photocopy of the CRFs will be sent to Boston and the original kept in Melbourne.

Melbourne, Boston and Glasgow will be responsible for identifying and chasing missing data in their region. Melbourne, Boston and Glasgow will keep all identifying data and be responsible for arranging follow-up within their region.

All chief investigators will have access to all data, but blinded to allocation.

10. QUALITY CONTROL

The WPPSI-III is an individually administered assessment. It takes 60-90 minutes to administer. Examiners will be trained and have prior experience administering and interpreting standardised assessments with infants. Typically examiners will have psychological training at the masters or doctoral level. At regular intervals the assessor will be video recorded during an assessment and the recording sent to [name] in Melbourne to compare assessment quality across sites.

11. ETHICS

There is a strong argument to believe equipoise exists in this trial. Awake regional and general anaesthesia are both accepted standards of care for inguinal hernia repair in children. Regional anaesthesia may be more technically demanding and preferences for one or the other may vary depending on the experience of the paediatric anaesthetist. In younger patients regional anaesthesia may be associated with less apnoea than general anaesthesia but this may be less apparent with the newer general anaesthesia agents. Similarly although there is animal data for toxicity, the evidence for risk of general anaesthesia is sufficiently weak to accept general anaesthesia as an arm in the study.

When recruiting patients the researcher approaching the patient must first ensure that both treating surgeon and anaesthetist are comfortable with randomisation.

All sites will obtain approval from their local Human Research Ethics Committees. In all cases written informed consent will be obtained from parents or guardians.

An independent Data Monitoring Committee and a Trial Steering Committee have been established to oversee the trial. Both committees have independent chairs and consist of statisticians, neonatologists, a psychologist and anaesthetists experienced in trial governance drawn from Australia, USA and Europe.

12. FINANCE AND INSURANCE

See attached budget in appendix II. Insurance will be provided by institutions where the study is being performed. For UK sites only Glasgow University will provide insurance to cover non negligent harm.

13. PUBLICATION POLICY

It is expected that the neurodevelopmental outcome at 2 and 5 years will be published in a high impact journal such as Lancet or New England Journal of Medicine. A number of other publications will result from secondary outcome analysis. All publication submissions will need TSC approval.

Appendix I

DEFINITIONS OF AGE

Calculating age is an imprecise science and there are various definitions in use. The dates cannot be exact but to avoid confusion the following definitions will be used:

Expected Date of Delivery (EDD): Date mother expected the child to be born – calculated *either* by 40 weeks after first day of last menstrual period, *or* from an early ultrasound scan, *or* 2 weeks plus date of conception if assisted reproduction

Gestational Age (GA): Calculated as: GA (in days) = 280 days - (Expected Date of Delivery – date of birth)

Chronological Age: Time elapsed since birth. Chronological age (in days) = date of randomisation – date of birth

Postmenstrual Age (PMA): PMA = Gestational Age + Chronological Age, Calculated as: PMA (in days) = date of randomisation – EDD + 280 days

Corrected Age: Chronological Age from Expected Date of Delivery

Inclusion criteria are:

- Gestational Age, 26 weeks or more ($GA \ge 182 days$)
- Postmenstrual Age, up to 60 weeks (PMA \leq 426 days)

By entering EED and date of birth, the randomisation program will automatically calculate Gestational Age and assign the child to the appropriate strata. If the calculated Gestational Age is less than 182 days or the Postmenstrual Age is greater than 426 days then an error message will appear and the child cannot be randomised.

Do not use the terms "Conceptual Age" or "Post Conceptual Age" and try to avoid using the term "Prematurity". When recording EDD, note on the CRF which method is used to calculate EDD (menstrual period, assisted reproduction or scan).

Note: the date of randomisation used in the program will be the current date Australian Eastern Standard Time.

Reference:

American Academy of Pediatrics Policy Statement. Age terminology during the Perinatal Period. *Pediatrics*. 2004;114:1362-1364.

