3. STUDY DESIGN

3.1 Experimental Design: Prospective, observer blind, multi-site, randomised, controlled, equivalence trial

3.2 Randomisation: Randomisation to either of the two treatment groups (GA or RA) will be by block and stratified by site and gestational age at birth. Gestational age at birth strata will be:

- 26 weeks to 29 weeks and 6 days
- 30 weeks to 36 weeks and 6 days
- 37 weeks and more

Access to randomisation numbers will be via a 24 hour web-based randomisation service set up and maintained by A/[name] at The Data Management & Analysis Centre, Department of Public Health, University of Adelaide, South Australia: http://www.dmac.adelaide.edu.au/gasRandomisation

Entry to the website is password protected.

3.3 Blinding: The anaesthetist will be aware of the group allocation. The psychologist and paediatrician performing the 2 and 5 year neurodevelopmental assessments will be blinded to study group. Parents will not be told which group their child was in but they will be allowed to discover the group and will be told if asked. Parents will be clearly instructed that if they do discover the group then they should not inform the assessing psychologist. A record will be made of whether or not the parents or the psychologist became aware of the allocation. The apnoea assessment and recovery assessment will not be blinded.

3.4 Study duration: The duration of subject participation is five years.

- Children will be enrolled before surgery.
- Data will be collected before and during anaesthesia and in the early postoperative period.
- Formal neurodevelopmental assessment will occur at 2 and 5 years corrected age (see appendix 1 for definition of corrected age).

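### The Appendix I rule for the expected date of delivery after assisted reproduction does not fit the protocol's own 280-day age scale; applied as written, it would shift gestational and postmenstrual age by +252 or -28 days

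*Protocol*

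**What the plan says.** Appendix I of the protocol gives three alternative routes to the EDD. The menstrual route is "40 weeks after first day of last menstrual period". The second is an early ultrasound scan. The third is "2 weeks plus date of conception if assisted reproduction".

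Whichever route is used, the EDD enters two formulas:

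- gestational age: "GA (in days) = 280 days - (Expected Date of Delivery – date of birth" (closing bracket follows);
- postmenstrual age: "PMA (in days) = date of randomisation – EDD + 280 days".

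The appendix then says: "By entering EED and date of birth, the randomisation program will automatically calculate Gestational Age and assign the child to the appropriate strata". An error message blocks randomisation "If the calculated Gestational Age is less than 182 days or the Postmenstrual Age is greater than 426 days". Corrected age, which times the 2- and 5-year assessments, is also counted from the EDD.

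Section 3.2 states: "Randomisation to either of the two treatment groups (GA or RA) will be by block and stratified by site and gestational age at birth". Sections 8.1 and 8.3 adjust the primary analysis for gestational age at birth, in the three categories used for stratification. Section 3.5.2 collects the mother's expected date of delivery and the birth date for randomisation. Section 3.5.4 and Appendix I have the CRF record how the EDD was obtained. No section corrects or restates the assisted-reproduction rule.

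**The concern.** The age scale counts from the last menstrual period: a child born on the EDD has a gestational age of 280 days. Conception comes about two weeks after that starting point, so the two weeks must be subtracted from the conception date before 40 weeks are added. The rule adds them instead, and does not mention the 40 weeks.

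The EDD feeds the lower gestational-age limit, the upper postmenstrual-age limit, the stratum, the gestational-age adjustment of the primary analysis and the timing of the primary outcome visit. Section 1.4.2 names prematurity as the most important potential confounder and treats stratification as indispensable. A wrong definition of this one date would therefore reach several parts of the trial for any infant to whom it was applied.

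**Working it through.** **Inputs.** All come from the protocol except one. Menstrual rule: EDD = last period + 280. Formulas: gestational age = 280 - (EDD - birth date); postmenstrual age = randomisation date - EDD + 280. Program limits: gestational age at least 182 days, postmenstrual age at most 426 days (60w6d). Strata (Section 3.2): 182-209, 210-258, and 259 or more days. Assumption not in the protocol: conception = last period + 14 days.

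**Reproducing the protocol's scale.** Let day 0 be the first day of the last period. The menstrual route puts the EDD on day 280. A birth on day 182 gives 280 - (280 - 182) = 182 days, and 26 x 7 = 182. The scale is consistent.

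**What the assisted-reproduction rule should give.** Conception is day 14, so a day-280 EDD is conception + 266 days (38 weeks). This leaves every age and stratum unchanged.

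**Literal reading: EDD = conception + 14.** The EDD falls on day 28.
- Shift in both ages: 280 - 28 = +252 days.
- A true 26w0d birth: 182 + 252 = 434 days.
- Postmenstrual age cannot be below gestational age, so it is at least 434, above 426. Every otherwise eligible infant is refused.

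**Carried-over reading: EDD = 40 weeks after (conception + 14) = conception + 294.** The EDD falls on day 308.
- Shift in both ages: 280 - 308 = -28 days.
- Highest true postmenstrual age admitted: 426 + 28 = 454 days (64w6d).
- Corrected age is understated by 28 days, so visits fall 28 days late.

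| True gestational age | Calculated (days) | Result |
|---|---|---|
| 26w0d-29w6d (182-209) | 154-181 | refused |
| 30w0d-33w6d (210-237) | 182-209 | lowest stratum instead of middle |
| 34w0d-36w6d (238-258) | 210-230 | stratum right |
| 37w0d-40w6d (259-286) | 231-258 | middle stratum instead of highest |
| 41w0d or more (287+) | 259+ | stratum right |

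**Sensitivity to the 14-day assumption.** If conception is day 14 + k, the shifts are +(252 - k) and -(28 + k). For k = -3 to +3 these are +255 to +249 and -25 to -31. Under the literal reading the lowest calculated age is still 182 + 249 = 431, above 426. Neither reading is rescued.

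**Scale of the precision loss (illustration only).** Suppose 2% or 5% of analysed infants were misplaced across the full 10-point gap between the preterm and term means in Section 8.3 (95 and 105). The residual variance rises at most from 225 to 225 + 0.02 x 100 = 227, or to 225 + 0.05 x 100 = 230, giving an SD of 15.07 or 15.17. With 598 infants and a true difference of 1 point, SE = SD x sqrt(4/598). Power = Phi(4/SE - 1.96) + Phi(6/SE - 1.96) - 1. This is 90.2% at SD 15, 89.9% at 15.07 and 89.5% at 15.17.

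**The case against.** The strongest reply is that few sites, perhaps none, would use the phrase to calculate a date. Appendix I introduces the EDD as the date the mother was expecting to deliver. Section 3.5.2 asks for that date, and no section lists a conception date among the data collected. A site that enters the EDD given clinically, or one from an early scan, is unaffected. The authors may have meant only that menstrual age is time since conception plus two weeks, which is the same convention used above to reach 266 days. This limits how often harm would occur. It does not repair the rule, because the text defines a delivery date and neither reading yields a correct one.

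It is also fair to say that the literal reading would reveal itself, since every affected infant triggers the error message. All the silent consequences (wrong stratum, late admission, late visits) rest on the carried-over reading, which imports 40 weeks from the neighbouring rule. That reading is plausible but inferred.

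A reader might infer three stronger things, none of which the documents support:

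- **That these infants are in fact being refused, admitted or stratified wrongly.** The documents do not show that any site applied the rule.
- **That a number of the 660 infants can be named, or that most errors would go unnoticed.** The protocol gives neither the share conceived by assisted reproduction nor their gestational ages, and refused infants are not among the 660.
- **That the comparison of the two anaesthesia groups is biased.** The EDD is fixed before allocation and the rule is the same in both arms.

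**Conclusion.** The definition is wrong as written. That rests on the protocol's own formulas and the usual two-week offset, and a few days either way makes no difference. The size per infant, if the rule is applied, is +252 days (literal, with visible refusal) or -28 days (carried over, with partly silent effects). The size for the trial cannot be stated, because neither the number of infants nor the sites' practice is given. Under the assumed 2-5% misplaced, the power loss is under one percentage point. The point therefore concerns eligibility, stratification, visit timing and a little precision. It deserves correction because the rule governs a date on which the program acts automatically, but it is no threat to the validity of the primary comparison.

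**What to change.** In Appendix I, replace the assisted-reproduction wording with: *or, if assisted reproduction, date of conception (fertilisation) plus 266 days (38 weeks)*. Send sites a short notice.

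For infants whose CRF records the assisted-reproduction method, compare the entered EDD with source records. The CRF alone will not do, because no conception date is listed as collected. Only where the faulty rule was used, correct the EDD, gestational age, postmenstrual age and corrected age.

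The stratum used at randomisation cannot be changed afterwards and should stay on record. Section 8.3 adjusts by the randomisation categories, so state in advance whether the adjustment uses the randomised or the corrected gestational-age category.

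Cost: one line of text, one notice and a check of a limited set of records. No extra infants or procedures are needed.

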Appendix II

We expect a little over half the children that are enrolled to be from Australia/NZ sites. We plan to use Australian grants to cover the costs of establishing the study and costs for recruitment and assessment within Australia/NZ. UK grants will cover costs in UK and US grants to cover costs in the UK.

The RA, psychologist and paediatrician labour costs will be reimbursed to each site as payment per child enrolled.

Grants

The Murdoch Childrens Research Institute has provided \$40,000 seed funding for this study. This will be spent meeting the costs for 2006 and part of 2007. [name] has been awarded an MCRI research fellowship to coordinate this study running for 3 years at 0.25 EFT salary support. We have also received \$48,000 from ANZCA.

We will apply for \$550,000 NH&MRC funding to cover direct costs of recruitment and assessment, and also to cover the salary at 0.25 EFT for [name] and [name] and 0.5 EFT for the project officer [name] for the duration of the study.

Boston Children's Hospital has already allocated funding to cover establishing the study in the US and recruiting in the Boston area. The US based investigators will also seek further specific US funding (FAER, SPA). In the UK, [name] is seeking funding in the UK from the HTA.

Similar to the Australian strategy with NHMRC funding, the US will apply for NIH and the UK for MRC funding. The likelihood of successfully receiving funds from NIH. MRC and NHMRC are expected to substantially increase once we have established recruiting and have preliminary data on apnoea.

Appendix III

TARGETS FOR STUDY

Period ending	Sites running	Patients recruited per period	Total recruited
1/12/2006	2	12	12
1/04/2007	9	70	82
1/10/2007	13	159	241
1/04/2008	15	177	418
1/10/2008	15	132	550
1/04/2009	15	110	660
